9.3.3 Analysis time point for primary endpoint

For the second part B (4th vaccination, cohorts 4-9), the primary endpoint analysis will be triggered as soon as for all patients data collection of the primary endpoint data (14 days after study vaccination) for all patients in part B has been finished. Analysis time (planned): October 2022 (primary endpoint analysis).

9.4 Secondary Endpoint Analyses

Summaries and analysis of the secondary endpoints will be based on the mITT population. If there are protocol deviations which may affect the analysis, a PP analysis may also be performed.

9.4.1 Secondary endpoints:

- Change in neutralizing antibody titre (Virus Neutralisation Assay) against wild-type 14 days after a 4th vaccination dose, to be determined in a subgroup only in which this type of assay has been performed.
- Change in neutralizing antibody titre (Virus Neutralisation Assay) **against variants of concern** 14 days after a 4th vaccination dose, to be determined in a subgroup only in which this type of assay has been performed.
- Antibody titre level **at 12 months** after a 4th vaccination dose measured by a quantitative enzyme-linked immunosorbent assay (anti-RBD-ELISA assay).
- Neutralizing antibody titre (Virus Neutralisation Assay) against wild-type SARS-CoV-2 at 12 months after a 4th vaccination dose, to be determined in a subgroup only in which this type of assay has been performed.
- Neutralizing antibody titre (Virus Neutralisation Assay) **against variants of concern** at 12 months after a 4th vaccination dose, to be determined in a subgroup only in which this type of assay has been performed.

For quantitative data the number of valid observations, mean, standard deviation, standard error, median, minimum and maximum will be calculated for each treatment group and each time point separately. Additionally, descriptive statistics of immunogenicity data may include Geometric Means (GM), Geometric Mean Fold Rise (GMFR) from baseline, and proportion of participants achieving a

pre-specified increase from baseline. Absolute values and the changes will be reported and visualized by individual trajectories of subjects over time via spaghetti plots. Furthermore, mean trajectories (such as means \pm sem) and boxplots will be provided.

9.4.2 Non-Inferiority of Geometric Mean titres

The geometric mean titres (GMT) following the 4th dose vaccination measured by quantitative enzyme-linked immunosorbent assay (Anti-RBD-ELISA) against wildtype virus at 14 days after the 4th dose will be compared between the boosters BNT162b2 and mRNA-1273 computing two-sided 95% confidence intervals for the GMR or differences of GMC on log scale (base 10). Based on the confidence intervals, an equivalence test will be performed. The equivalence margins are the 1.5 to 0.67-fold change between the GMT in the two boost arms corresponding to a margin for the differences of GMC on log scale (base 10) which results in a margin ± 0.174 . This is suggested in Section 2.3.1 of the EMA/117973/2021 Reflection paper on the regulatory requirements for vaccines intended to provide protection against variant strain(s) of SARS-CoV-2¹¹. Because GMT are expected to have a skewed distribution, the log10 scaled GMT values will be compared using a linear model with factors booster (BNT162b2/mRNA-1273) as well as the stratification variables used in the randomisation. As this is a secondary analysis, no adjustment for multiplicity will be made.

9.4.3 Linear Models & Adjustment for Covariates and Mixed Models

When analysing the data from all study visits (e.g., Visit 1, Visit 2 and Visit 5 for immunogenicity data such as Anti-RBD or anti-N IgG), mixed model for repeated measurements (MMRMs) will be applied using subject ID as random factor using an unstructured covariance matrix. The last value before randomisation (baseline) will be used as covariate in the MMRM.

Similarly as described for the logistic regression models for the primary endpoint (see supportive analyses for the primary endpoint), also in the MMRs we adjust for factors/covariates such as initial vaccination regimens (factor cohort), age and sex. We will also address for the different time lags to previous vaccinations, e.g., for the time between the 2nd and 3rd doses and between the 3rd and 4th doses, respectively in further sensitivity analysis, e.g., including the number of days between vaccinations as additional covariate in the analysis models.

The impact of new covid infections after baseline on the secondary endpoints will be explored similarly to the primary endpoint analysis. For example by using an additional factor (New Covid Infections based on anti-Nucleocapside IgG between visits) in the MMRMs and performing analysis on the PP analysis set.

In further secondary analyses, it will be explored whether switching or keeping the same vaccine product for the 4th vaccination (study intervention in B) compared to the 3rd vaccination will have an effect. To evaluate such an impact models will be performed using for example the interaction between cohort and study drug or an indicator variable whether the 4th and 3rd vaccination are the same or not.

In addition to using the log10 scaled GMT values (=y) as dependent variable, we will use the relative change compared to the baseline value as dependent variable. The relative change is defined as $(Y_{\text{visit}} - Y_{\text{baseline}}) / Y_{\text{baseline}}$. The change might be presented as percentage change.

The secondary analyses will be performed overall and for cohorts separately.

9.5 Exploratory analyses

Additional to the primary and secondary immunogenicity endpoints, exploratory endpoints include:

- Change in cellular immune response (CD4+ and CD8+ T cell response) measured by qPCR 14 days after 4th booster dose, to be determined in a subgroup only in which this type of assay has been performed.
- Neutralizing antibody titre (Virus Neutralisation Assay) against newly emerging variants in bio-banked samples in a subgroup analysis after 4th vaccination dose. To be determined in a subgroup only in which this type of assay has been performed.
- Correlates of humoral immune response, cellular immune response and viral neutralising capacity against SARS-CoV-2 variants of concern (VOCs), to be determined in a subgroup only in which this type of assay has been performed.

Different combinations of vaccines (1st, 2nd, 3rd and the on-study 4th vaccine dose) will be assessed for equivalence in terms of humoral and/or cellular immune response against VOC compared to approved homologous COVID-19 vaccination schedules. The analysis strategy will be performed as described for the primary and secondary endpoints (see sections 9.1.3 and 9.1.4)

Furthermore, exploratory comparisons of the primary endpoint as well as the humoral and/or cellular immune response against VOC will be performed between cohorts as well as between the treatment groups within cohorts.

Correlations between different antibody titre values

To visualize whether there is a correlation between laboratory and demographic data at specific visits, such metric data will be visualised via scatterplots. Correlation coefficients by Pearson and

Spearman will be reported. The correlation analysis will be performed for both absolute values and changes (=difference between two visits).

Optional analysis:

As an option it is planned to perform comparisons with the control group from EU-COVAT subprotocol with the EudraCT no.: 2021-004889-35. The control group of EU-COVAT subprotocol EudraCT no. 2021-004889-35 will be only utilised if the sample size in the age group of interest is sufficiently large. Otherwise, the data of the control group will be reported only descriptively. These analyses will be performed similar to the analysis described in 9.1.4. and 9.1.6. If such analyses are actually performed the details of the analysis will be stated in the report.

9.6 Data Transformations

The data will be visualised by histograms. Skewed laboratory data will be transformed using appropriate functions such a log, log10 or sqrt. The transformations will be noted in the final report.

For laboratory values:

For values below the Lower Limit of Detection (LLOD) we will impute a value equivalent to LLOD/2 if such a value is marked by the laboratory and the LLOD value provided. Laboratory values that are reported as above the LLOD but below the Lower Limit of Quantification (LLOQ) will be kept as reported by the corresponding Laboratory if actual numerical values are provided. If actual values below the LLOQ are not provided, the observations will be replaced with a value equivalent LLOQ/2. Values that are greater than the upper limit of quantification (ULOQ) will be kept when actual values are reported from the corresponding laboratory, otherwise the ULOQ if provided by the laboratory and the value is marked.

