6.1.3. Primary analysis

All primary analyses will be on the mITT set. The primary endpoint is the rate π of 2-fold antibody titre increase following the 4th vaccine dose measured by quantitative enzyme-linked immunosorbent assay (Anti-RBD-ELISA) against wildtype virus at 14 days after the 4th vaccine dose (versus immediately before vaccination).

For the binary primary endpoint absolute and frequencies in percent will be calculated for each study part (Part A, Part B) and treatment group. For each study part and treatment group the corresponding rate together with simultaneous 95% confidence intervals will be calculated. Exact Clopper Pearson confidence intervals at Bonferroni adjusted level of $(1-0.05/2) * 100\%$ will be provided.

In additional supportive analysis, the primary endpoint will be performed in the same way for each cohort separately, i.e., further exploratory analyses will be performed based on different pre-vaccination series. Especially, within each cohort the multiplicity adjustment will be implemented.

The data will be visualised with bar charts.

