9.3 Primary Endpoint Analysis

All primary analyses will be on the mITT set, consisting of all randomised subjects whose primary endpoint measurement is available. The primary endpoint is the rate π of 2-fold antibody titre increase following the 4th vaccine dose measured by quantitative enzyme-linked immunosorbent assay (Anti-RBD-ELISA) against wildtype virus at 14 days after the 4th vaccine dose (versus immediately before vaccination).

For the binary primary endpoint absolute and frequencies in percent will be calculated for each intervention group in Part B. For each treatment group in part B the corresponding rate together with simultaneous 95% confidence intervals will be calculated. Exact Clopper Pearson confidence

intervals at Bonferroni adjusted level of $(1-0.05/2) * 100\%$ will be provided (as there are two treatment groups in part B).

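### When the laboratory gives no number above the ULOQ, SAP 9.6 scores a participant with a baseline above ULOQ/2 and a day-14 value above the ULOQ as a non-responder, although the true status is unknown

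*SAP*

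**What the plan says.** SAP 9.3 states the endpoint as "The primary endpoint is the rate π of 2-fold antibody titre increase following the 4th vaccine dose", measured by anti-RBD ELISA at day 14 "versus immediately before vaccination". Protocol 6.1.3 has the same definition. Each participant's status is therefore a ratio of two titres compared with 2. Neither document says whether a ratio of exactly 2 counts.

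SAP 9.6 is the only rule for values outside the assay range, and it does not exempt the responder endpoint. It has three parts:

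- Below the LLOD: "we will impute a value equivalent to LLOD/2 if such a value is marked by the laboratory and the LLOD value provided".
- Between LLOD and LLOQ: values "will be kept as reported by the corresponding Laboratory if actual numerical values are provided"; otherwise, "If actual values below the LLOQ are not provided, the observations will be replaced with a value equivalent LLOQ/2".
- Above the ULOQ: values "will be kept when actual values are reported from the corresponding laboratory, otherwise the ULOQ", provided the laboratory supplies the limit and marks the value.

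Substitution is thus a fallback for results that arrive without a number. The supportive and sensitivity analyses of the primary endpoint (SAP 9.3.1 and 9.3.2) deal with cohort, age, sex, dose intervals, new infections and the per-protocol set. None deals with titres beyond the assay limits.

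**The concern.** A single substituted value may be tolerable in a summary of titres. In a ratio with a fixed cut-off it can decide the outcome. Once day 14 is capped at the ULOQ, the largest ratio a participant can show is ULOQ divided by baseline. Participants with high pre-dose titres may then be unable to count as responders.

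The situation is plausible in this trial. Everyone enters with three doses, the last possibly only a month earlier, and is sampled 14 days after a fourth. At stake is the headline result, the responder rate per group with its exact interval. That interval describes sampling error only, so a systematic loss at the assay ceiling would not show in it.

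**Working it through.** **The plan's own figure.** Sample size section: n = 250 per group, rate 0.50, two-sided alpha 0.05/2 = 0.025. Half-width = 2.2414 × sqrt(0.25/250) = 0.0709. The stated 7.1 points reproduces. It serves below as a yardstick.

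**Scoring individual records.** The limit ULOQ = 1000 is illustrative.

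| Baseline | True day 14 | Number reported above ULOQ? | True ratio | Scored ratio | Scored as |
|---|---|---|---|---|---|
| 501 | 5000 | no | 9.98 | 1000/501 = 1.996 | non-responder |
| 501 | 5000 | yes | 9.98 | 9.98 | responder |
| 999 | 5000 | no | 5.005 | 1000/999 = 1.001 | non-responder |
| 2000 | 9000 | no | 4.5 | 1000/1000 = 1.0 | non-responder |
| 2000 | 9000 | yes | 4.5 | 4.5 | responder |

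**Which pairs are affected.** If day 14 is at or below the ULOQ and baseline is above ULOQ/2, the true ratio is below 2 and the scoring is right. If day 14 is above the ULOQ and baseline is at or below ULOQ/2, the true ratio exceeds 2 and the scored ratio is at least 2, again right. (At a baseline of exactly ULOQ/2 the scored ratio is 2.0, so this needs 2-fold to mean at least 2.) Only one combination remains: day 14 known only to exceed the ULOQ, with baseline above ULOQ/2 or itself above the ULOQ. Its true status is unknown and its scored status is always non-response. The error therefore runs in one direction.

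**Size under an assumed model.** The documents give no limits or SDs, so every input here is an assumption: baseline log10 SD 0.45; log10 rise = log10(GMFR) - 0.3 × baseline + residual with SD 0.25; geometric mean fold rise (GMFR) 3 in one arm and 4 in the other; no numbers reported above the ULOQ.

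True rates: the SD of the log rise is sqrt(0.25² + (0.3 × 0.45)²) = 0.284. For GMFR 3, z = (0.477 - 0.301)/0.284 = 0.62, giving 73.2%. For GMFR 4, z = (0.602 - 0.301)/0.284 = 1.06, giving 85.5%.

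Scored rates, by simulation with both visits capped at the ULOQ:

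| Day-14 values above ULOQ | Scored, GMFR 3 | Scored, GMFR 4 | Loss (points) |
|---|---|---|---|
| 5% | 72.6% | 84.5% | 0.6 and 1.0 |
| 10% | 71.7% | 83.1% | 1.5 and 2.4 |
| 20% | 69.2% | 79.7% | 4.0 and 5.8 |
| 40% | 62.1% | 70.3% | 11.1 and 15.2 |

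Pairs of unknown status make up about 3%, 7-8% and 18-20% of participants in the last three rows. Adding them back as responders at 20% gives about 69.2 + 7 = 76% and 79.7 + 8 = 88%. The true 73.2% and 85.5% then lie between the two versions of each rate. The between-arm difference falls from 12.3 points to 11.5, 10.4 and 8.2 at 10, 20 and 40%.

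**Cross-check by a simpler model.** Let c be the share of baselines above ULOQ/2, with no numbers above the ULOQ, and let response be independent of baseline with true rate p. Every responder in that share is lost, so the scored rate is p(1 - c). The loss reaches 7.1 points at c = 0.071/p: 14.2% for p = 0.5, 10.1% for p = 0.7 and 7.9% for p = 0.9. If high baselines respond less (correlation -0.5 between baseline and log rise), the loss is smaller: 0.50 falls to 0.48 at c = 10% and about 0.46 at c = 20%.

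**The case against.** **The rule is only a fallback.** SAP 9.6 keeps actual values when the laboratory reports them. A reader might infer that a baseline above ULOQ/2 can never respond in this trial. The text does not support that, because with numbers reported the effect vanishes. This stands, and the point is conditional for that reason.

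**The size is unknown.** It depends on the assay limits, the reporting format and any dilution of high samples. Protocol section 3.10, on the study laboratories, was not available for this check, so silence there cannot be held against the plan. At 5 or 10% above the ULOQ, the modelled loss is well inside 7.1 points. This also stands. The largest figures need 40% of day-14 values beyond the limit, none with a number.

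**The arm comparison is not the primary result.** SAP 9.8 gives it secondary standing, and the Cochran-Mantel-Haenszel and logistic analyses are supportive. Agreed: the primary consequence is the rate in each group.

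**The lower limit.** Because LLOQ divided by LLOQ/2 is exactly 2, a reader might infer that the bottom rule manufactures responders on a comparable scale. Single records can be mis-scored this way: 9.9 to 10 with LLOQ 10 scores 2.0 if no number is reported and 2-fold includes 2. Under the same boosting model, however, with 2-10% of baselines below the LLOQ, the group rate moves by only about 0.1 point or less, because nearly all those participants truly respond. Shifts of 0.6-2 points come from assuming no true rise at all. A model with rise unrelated to baseline, fold-rise SD 0.35, baseline SD 0.3 and GMFR 2 gives 51.7% against 50.1%, but needs one baseline in ten below the LLOQ. Nothing in the documents suggests that after three doses.

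Scoring low baselines against the full LLOQ would be worse. At GMFR 3 with 10% below the LLOQ, the true rate is 73.3%, the SAP rule gives 73.4% and that alternative 71.5%. Applied to every baseline below the LLOQ, it would also overwrite reported numbers that 9.6 keeps.

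**Conclusion.** The point holds for the upper limit, and only where day-14 results arrive as above the ULOQ without a number. In that case 9.6 assigns non-response to every participant whose baseline exceeds ULOQ/2, although the data cannot show whether the titre doubled. The responder rate is biased downward, the exact interval does not reflect it, and no planned sensitivity analysis would reveal it.

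The modelled loss runs from about 0.6-1.0 points (5% of day-14 values above the ULOQ) to 11-15 points (40%). These figures rest on the assumed SDs, slope and fold rises, and cannot be narrowed from the documents. The planned precision of 7.1 points and the total of 550 are unaffected. The lower-limit rule needs no change on this ground.

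This is a specific, cheap improvement to the scoring of the primary endpoint. It does not show that the result will be materially wrong.

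**What to change.** Add to SAP 9.3 and 9.6, for fold-rise responder endpoints only:

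1. If day 14 is reported only as above the ULOQ, and baseline is above ULOQ/2 or also reported only as above the ULOQ, classify the participant as unresolved.
2. Report the number unresolved in each group. Give each group's rate and Clopper-Pearson interval twice: with unresolved participants all counted as non-responders (the current rule) and all as responders.
3. State that 2-fold means a ratio of at least 2.
4. Apply the same rule to any other proportion based on rise from baseline under SAP 9.4.1.

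No separate rule is needed for a baseline at or below ULOQ/2 with day 14 above the ULOQ: with item 3 in place, 9.6 already scores it as a response. The lower-limit rules can stay as they are.

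The cost is SAP wording and one extra pair of rates per group, with no new samples, visits or participants. If many values exceed the ULOQ, the primary result becomes a range instead of a single rate. Because the trial is unblinded and SAP section 9 foresees no blind data review, the wording should be settled before primary results are seen.

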Different types of AEs will be grouped. Additionally the safety data will be reported descriptively for each intervention and cohort separately.

11 Software program(s):

All statistical analyses will be conducted with statistical software like SAS 9.4. (or higher) and R 3.6.3. (or higher).

12 Sample size calculation

The number needed has been calculated at 550 for part B (i.e., 600 overall for Part A and B, and including a potential dropout rate of 8-10% for Part B).

12.1 Sample size calculation with multiplicity adjustment:

Sample size calculation has been carried out for the primary endpoint for the rate π of 2-fold antibody titre increase following 4th dose vaccination. As two-sided simultaneous 95% confidence intervals for this rate should be calculated separately for each randomized group in Part B a Bonferroni adjustment was used in the sample size calculation accordingly.

When the sample size is 250 per randomized group, two-sided simultaneous 95% confidence intervals (with Bonferroni adjustment for 2 simultaneous confidence intervals in a cohort) for a proportion using the large sample normal approximation will extend no more than $\pm 7.1\%$ (percentage points) from the observed proportion. E.g., if the observed proportion is 50% (where the confidence interval is widest), the confidence interval ranges from about 42.9% to 57.1%.

To adjust for potential dropouts in part B of about 8-10%, the total sample size for part B (=4th vaccination and Cohorts 4-9) was set to 550.

In the table below the precision for the simultaneous two-sided 95%-confidence intervals (with the same assumptions as described above) is shown for varying sample sizes. This shows which precision could be achieved in the different cohorts based on the previous vaccination strategy (see also inclusion criteria for Part B).

Sample Size, n	250	200	150	125	90	50	40
Expected Proportion, π	0.500	0.500	0.500	0.500	0.5	0.500	0.5
Distance from Proportion to Limit, ω	0.071	0.079	0.092	0.100	0.118	0.158	0.177

Also, the sample size of n=550 in part B shall provide adequate power for comparison in GMT (Geometric mean titre values) between the two randomised treatment arms in aged patients, e.g., comparison of different boosting strategies depending on the initial vaccination. E.g., demonstration of equivalent immune response after heterologous boosting, in comparison with the homologous approach, will facilitate vaccination programs when vaccine availability is an issue.

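### If more than a few percent of day-14 titres are reported only as >ULOQ, substituting the ULOQ can let the equivalence test pass too often when the true ratio is near the margin

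*SAP*

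**What the plan says.** SAP 9.6 (Data Transformations) has two steps for results above the ULOQ. They "will be kept when actual values are reported from the corresponding laboratory"; failing that, the analysis uses "otherwise the ULOQ if provided by the laboratory and the value is marked". The rule covers laboratory values in general, so it covers the day-14 anti-RBD titres. Appendix A, section 16.8, repeats it for Part A.

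SAP 9.4.2 compares day-14 titres between BNT162b2 and mRNA-1273 on the log10 scale. It uses a linear model with booster and the randomisation strata as factors, and a two-sided 95% interval. "Based on the confidence intervals, an equivalence test will be performed". The limits are stated as follows: "The equivalence margins are the 1.5 to 0.67-fold change between the GMT in the two boost arms", given as ±0.174 on the log10 scale. The section adds: "As this is a secondary analysis, no adjustment for multiplicity will be made".

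Neither document gives the ULOQ, an expected share above it, a rule for re-diluting over-range samples, a censored-data model, or a sensitivity analysis for substituted values.

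**The concern.** A result known only to exceed the ULOQ is a right-censored observation. Setting it equal to the ULOQ turns a lower bound into a measurement. If one group has higher titres, more of its values are clipped, so the difference in log means shrinks. The clipped SDs are also smaller, so the interval narrows. In a superiority test the first effect would be conservative. In an equivalence test both effects favour the conclusion being tested.

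A group difference is plausible on the documents' own account. Protocol 4.7.6.1 justifies the mRNA-1273 dose used in the trial partly by a possible gain in immunogenicity. SAP 12.1 says that showing equivalence would help vaccination programmes, and SAP 9.5 carries the same analysis strategy into the exploratory equivalence comparisons. SAP 9 rules out a blind data review, so there is no later step at which the handling could be settled without sight of group results.

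The 2-fold endpoint is exposed in one corner. If the day-14 result is only >ULOQ and the baseline is above ULOQ/2, the substituted ratio ULOQ/baseline is below 2. The participant then counts as a non-responder although the true ratio is unknown. If the baseline is at or below ULOQ/2, the substituted ratio is at least 2 and the classification is right.

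**Working it through.** **Inputs from the documents.** Group size, SAP 12.1: "When the sample size is 250 per randomized group". Interval and margin: SAP 9.4.2.

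**Assumptions, because the documents give no figure.** SD of log10 titre 0.3 to 0.6. Share of day-14 values above the ULOQ and without a number, both groups pooled, 0% to 50%. Normal log10 titres with a common SD and no covariates.

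**The plan's own figures reproduce.** The half-width of the Bonferroni-adjusted interval at 50% is 2.2414 × √(0.25/250) = 0.0709, the stated 7.1 points. The margin is log10(0.67) = −0.1739 (log10(1.5) = 0.1761), so ±0.174 is right and corresponds to a ratio of 1.49. No sample-size or power figure is given for the equivalence test.

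**Formulas.** Let X be normal with mean μ and SD σ, clipped at c, and let z = (c − μ)/σ.
- E[min(X,c)] = μΦ(z) − σφ(z) + c(1 − Φ(z))
- E[min(X,c)²] = (μ² + σ²)Φ(z) − σ(μ + c)φ(z) + c²(1 − Φ(z))
- D is the difference of the two clipped means, and SE = √((s₀² + s₁²)/250), with s₀ and s₁ the clipped SDs
- P(pass) = Φ((0.174 − D)/SE − 1.96) − Φ((−0.174 − D)/SE + 1.96)

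The true difference is set at the margin, 0.174. Without clipping, D = 0.174 and P(pass) = Φ(−1.96) = 2.5%; the second term is negligible.

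**One cell in full (SD 0.4, 20% clipped).** The ULOQ lies 0.432 above the lower group's mean and clips 14.0% of the lower group and 26.0% of the higher. The clipped means are −0.0286 and 0.1112, so D = 0.1398 and the ratio is 10^0.1398 = 1.38. The clipped SDs are 0.353 and 0.314, so SE = √((0.1244 + 0.0983)/250) = 0.0298, against 0.0358 unclipped. P(pass) = Φ(0.0342/0.0298 − 1.96) = Φ(−0.81) = 21%.

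**All settings, true ratio 1.49:**

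| Clipped | Expected GMR | SD 0.6 | SD 0.5 | SD 0.4 | SD 0.3 |
|---|---|---|---|---|---|
| 0% | 1.49 | 2.5% | 2.5% | 2.5% | 2.5% |
| 1% | 1.49 | 2.7% | 2.7% | 2.8% | 2.8% |
| 2% | 1.48 | 2.9% | 3.0% | 3.1% | 3.3% |
| 5% | 1.46-1.47 | 3.6% | 3.9% | 4.3% | 4.9% |
| 10% | 1.44 | 5.4% | 6.1% | 7.4% | 9.8% |
| 20% | 1.38 | 12% | 15% | 21% | 32% |
| 30% | 1.32-1.33 | 25% | 34% | 48% | 72% |
| 50% | 1.22 | 79% | 91% | 99% | 100% |

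**Simulation, 4,000 trials per setting.** At SD 0.4, substitution passed in 5.0%, 7.8%, 19.8%, 48.4% and 98.3% of trials at 5%, 10%, 20%, 30% and 50% clipped. A right-censored normal (Tobit) fit to the same data passed in 2.3% to 3.3% over SD 0.4 and 0.5, with a mean ratio of 1.49 to 1.50. With t(5) errors at 10% and 30% clipped, substitution gave 6.3% and 41.1%, and the censored fit 3.1% and 2.2%.

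**Away from the margin (SD 0.4; 10%, 20%, 30% clipped).** A true ratio of 1.7 passes in 0.1%, 0.9% and 6.3% of trials. A true ratio of 2.0 passes in at most 0.03%, although its estimate falls to 1.88 at 10% and 1.63 at 30% clipped.

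**Unequal spread.** With equal log means and SDs of 0.3 and 0.5, clipping 10% and 30% gives expected ratios of 0.92 and 0.85, so here the estimate moves away from 1. A censored fit with one common variance was also biased: about 0.95 and 0.87 in a simulation with the ULOQ set to clip 10% and 30% of the SD 0.3 group (about 16% and 34% of all values). A censored model with a separate variance per group is correctly specified in this case.

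**The case against.** The strongest reply is that the rule is only a fallback. Numeric values are kept, the assay is described as quantitative, and no section says that results come back as >ULOQ. If over-range samples are diluted and quantified, nothing is clipped. Protocol 4.9.3 mentions a separate laboratory manual, but describes it as covering preparation, storage and logistics, and it is not available here. This reply stands as a limit on size: the clipped share could be zero, and at 1-2% the effect is negligible. It does not remove the point, because the SAP foresees such results and says how to analyse them.

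A reader might go further in four ways that the documents do not support.
- That the planned equivalence test is anti-conservative as it stands. This needs a clipped share that neither document gives.
- That it is the only formal comparison of the groups. SAP 9.3.1 plans a stratified Cochran-Mantel-Haenszel test and a logistic regression, and the equivalence test is secondary.
- That the primary 2-fold rate is lowered. This needs a baseline above ULOQ/2 together with a day-14 result without a number, and no frequency is known for that pair.
- That clipping always pulls the ratio toward 1 and any censored regression cures it. The unequal-spread case contradicts both.

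The Part A copy of the rule adds little weight, since Part A is exploratory after early closure.

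**Conclusion.** The concern holds conditionally. If one group's titres are stochastically higher, clipping both at the same value can only shrink the difference in log means; this does not need normality. The false-pass rates do rest on normal log10 titres, similar spread, 250 per group, a true ratio at the margin, and assumed SDs and clipped shares.

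On those assumptions the error rate is close to nominal at 1-2% clipped, up to twice nominal at 5%, two to four times nominal at 10%, and far above it from 20%. The harm is concentrated near the margin: a true twofold ratio is practically never declared equivalent. Since the share is unknown and a better analysis is cheap, the plan should specify it now and not wait to see the share.

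**What to change.** In SAP 9.6 and 9.4.2:
- Keep numeric values above the ULOQ as now.
- Where only `>ULOQ` is reported, base the day-14 ratio and the equivalence interval on a right-censored regression of log10 titre with the same factors and group-specific variances.
- Show the ULOQ-substituted analysis as a sensitivity analysis.
- Report the number of clipped values by group and visit.

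For the 2-fold endpoint, keep the pre-specified rule as the single primary estimate. Add one sensitivity analysis that counts as responders those participants with a baseline above ULOQ/2 and a day-14 result reported only as `>ULOQ`. The two results bound the effect of these participants.

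The cost is SAP wording and a standard procedure in SAS or R, with no new data or visits. If the laboratory returns numbers for every sample, there are no censored results and the censored-data step does not come into play. The downside is that the censored model relies on the assumed shape of the upper tail, which is why the substituted result should stay visible beside it.
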